HgbA1C	Glycated hemoglobin
IB	Investigators Brochure
ICF	Inform Consent Form
ICH	International Conference on Harmonization of Technical Requirements for Registration of Pharmaceuticals for Human Use
IEC	Independent Ethics Committee
█	█
IN	Investigator Notifications
IRB	Institutional Review Board
IRT	Interactive Response Technology
IU	International units
i.v.	Intravenous
LBM	Lean body mass
LFT	Liver function test (raised serum transaminases and/or bilirubin levels)
█	█
LLOQ	Lower Limit of Quantification
MedDRA	Medical dictionary for regulatory activities
mSv	Milisieverts per hour (background radiation measurement)
OC/RDC	Oracle Clinical/Remote Data Capture
QA	Quality Assurance
QTcF	Fridericia QT correction formula
█	█
PBO	Placebo
PD	Pharmacodynamics
█	█
█	█
█	█
PP	Per-protocol
█	█
RBC	Red cell count
SAE	Serious adverse event
SAF	Safety set
SD	Standard deviation

	
sIBM	sporadic inclusion body myositis
SPPB	Short Physical Performance Battery
μSv	Microsieverts per hour (ionizing radiation measurement)
WBC	White cell count
WHO	World Health Organization
γ-GT	γ-Glutamyltransferase
6MWT	6 Minute Walk Test

Glossary of terms

Assessment	A procedure used to generate data required by the study
Enrollment	Point/time of patient entry into the study at which informed consent must be obtained (i.e. prior to starting any of the procedures described in the protocol)
Epoch	A portion of the study which serves a specific purpose. Typical Epochs are: screening/recruitment, wash-out, treatment, and follow-up
Investigational drug	The drug whose properties are being tested in the study; this definition is consistent with US CFR 21 Section 312.3 and is synonymous with “investigational new drug” or “investigational medicinal product.”
Investigational treatment	All investigational drug(s) whose properties are being tested in the study as well as their associated treatment controls. This includes any placebos, any active controls, as well as approved drugs used outside of their indication/approved dosage or tested in a fixed combination. Investigational treatment generally does not include protocol-specified concomitant background therapies when these are standard treatments in that indication
Medication number	A unique identifier on the label of each investigational/study drug package in studies that dispense medication using an IRT system
Protocol	A written account of all the procedures to be followed in a trial, which describes all the administrative, documentation, analytical and clinical processes used in the trial.
Randomization number	A unique identifier assigned to each randomized patient, corresponding to a specific treatment arm assignment
Patient Number	A number assigned to each patient who enrolls into the study
Variable	A measured value or assessed response that is determined in specific assessments and used in data analysis to evaluate the drug being tested in the study

Protocol summary

Protocol number	CBYM338E2202E1
Title	A 24-week off drug extension parallel group study assessing the durability of effect on skeletal muscle strength and function following a 6-month double blind placebo controlled study evaluating bimagrumab in older adults with sarcopenia
Brief title	A 24-week off drug extension study assessing the durability of effect of bimagrumab in older adults with sarcopenia previously participating in the 6-month core study
Sponsor and Clinical Phase	Novartis Phase IIb
Investigation type	Drug
Study type	Interventional
Purpose and rationale	The purpose of this extension study is to evaluate the durability of effect on skeletal muscle mass, strength and physical function upon discontinuation of treatment received in the core study
Primary Objective(s)	
 The primary objective is to assess the durability of effect of bimagrumab (BYM338) as measured by the short physical performance battery (SPPB) total score at week 49.
Secondary Objectives	
 To evaluate the safety and tolerability of bimagrumab following treatment withdrawal as assessed by measures such as vital signs, clinical laboratory variables, electrocardiogram (ECG), and adverse events (AE). To evaluate the durability of effect of bimagrumab at week 49 as measured by: 
 6 minute walk test (6MWT) mobility as measured in gait speed (GS) over 4 meters total lean body mass (LBM) and appendicular skeletal muscle index (ASMI) measured by dual energy X-ray absorptiometry (DXA)
Study design	This Phase IIb extension study is a 24 weeks off drug study following 24 weeks of treatment in the core study (CBYM338E2202) in older patients with sarcopenia.
Population	The study population will be community-dwelling men and women ages 70 years and older completing the full study treatment period (24 weeks) of the core study (CBYM338E2202) and willing to enter CBYM338E2202E1.
Inclusion criteria	
 Men and postmenopausal women aged 70 years or older that have participated in, and have completed the full study treatment period per protocol (24 weeks) in the preceding core study (CBYM338E2202) Written informed consent must be obtained before any assessment of the extension study is performed (can be obtained at the End of Treatment (EOT) visit of the core study).
Exclusion criteria	Any condition which should have led to treatment discontinuation per protocol in the core study.

Investigational and reference therapy	none
Efficacy assessments	
• 6MWT to assess functional improvement• SPPB to assess physical functional improvement• Usual GS to assess physical functional improvement• LBM and ASMI assessed by DXA to measure total and regional lean body mass. 
█ [REDACTED]
 
█ [REDACTED]

Safety assessments	
• Physical examination• Vital signs• Weight• Laboratory evaluations• ECG
Data analysis	Summary statistics by treatment arm will be provided for the primary endpoint and continuous secondary endpoints. A 95% confidence interval for the difference between each continued bimagrumab dose arm vs. corresponding placebo switched from the same bimagrumab dose will be calculated at each visit.
Key words	Durability of effect, safety of bimagrumab in patients with sarcopenia.

Amendment 1 (26-Apr-2017)

Amendment rationale

The purpose of this amendment is to revise the extension study design to align it with changes recently implemented in the core study CBYM338E2202 while maintaining and further focusing the primary purpose of the extension study to evaluate the durability of effect of 24 weeks of bimagrumab therapy upon treatment discontinuation.

The original study was designed to evaluate several questions i.e. how long the potential effect of 24 weeks of bimagrumab treatment would be maintained following treatment discontinuation and if a 48 weeks continuous treatment would provide additional benefit over a 24 weeks treatment period. The randomized withdrawal feature of the design reduced the sample size of each treatment arm with the risk of not being able to address the questions. Novartis with this amendment is removing this withdrawal randomization feature and is refocusing the study on one main question: how long the potentially observed effects after 24 weeks of treatment with bimagrumab will last once the treatment is discontinued? Therefore, all newly enrolled patients in this extension study will be followed off drug for a period of 24 weeks. As a consequence, the size of each treatment arm will remain as per study entry and not reduced as the withdrawal randomization would otherwise do. Questions no longer addressed by this study may be addressed at later stage of the bimagrumab clinical development program if they are still relevant.

Patient visits over the 24 weeks are reduced from seven to three since there is no need for on-site infusion every 4 weeks. This should substantially reduce patient burden and facilitate study acceptance. However in order to promote patients' engagement and adherence to the study, there is a required exercise program [REDACTED] and, monthly phone calls will be made to patients.

Patients active in the study upon implementation of this protocol amendment will remain on the original protocol visit schedule which reflects the randomized withdrawal design. This way all patients enrolled in this study prior to this protocol amendment will have a similar journey and even if the sample is small (estimated to approx. 45 patients) this sub-group of patients will provide valuable information on the effect of prolonged treatment for 49 weeks. At the time of this protocol amendment's implementation it is anticipated that 10 to 15 patients will be on going and will continue being dosed while newly enrolled patients will be followed off drug under a revised visit schedule.

The end of part A in the core study will trigger an interim analysis of the extension study data available at that time. Data from this extension study will be combined with the core study data and will enable decision making on the rest of the program. In addition, following this interim analysis, the global study team will be unblinded to the individual treatment codes from those patients included in this analysis. However, Novartis associates in the countries and site personnel will remain blinded to the treatment codes until the final study data base lock.

The rationale for the changes implemented in the core study such as the change of primary endpoint, the reduction of the cardiac safety monitoring, [REDACTED]

[REDACTED] are described in the core protocol amendment #2 (CBYM338E2202).

At the time of this amendment, approximately 45 patients have been enrolled in the study.

[REDACTED]

Changes to the protocol

Changes to specific sections of the protocol are shown in the track changes version of the protocol using ~~strike through red font for deletions~~ and red underlined for insertions.

The informed consent of the study will be amended. A copy of this amended protocol will be sent to the Institutional Review Board (IRB)/Independent Ethics Committee (IEC) and Health Authorities.

The main changes are the following:

- Re-focus of the study on assessing the durability of effect of bimagrumab over a 24 week period *off* drug. As a result the withdrawal randomization design feature is removed and all newly enrolled patients are followed off drug, while patients previously enrolled will complete the study more or less as per the original visit schedule
- Study is reduced to 24 weeks with site visits every 12 weeks instead of every 4 weeks and phone calls have been added in between visits to promote adherence and to record [REDACTED] other associated feedback from study participants.
- Addition of a planned interim analysis
- The need for unblinding of core treatment code for newly enrolled patients will follow the core study protocol procedure.
- All IMP related sections are only applicable to those patients enrolled under the original protocol version
- Inclusion/exclusion criteria were simplified as only patients willing and having fully completed the 24 weeks of core study treatment are eligible
- As part of the alignment between the core and the extension studies, the following key changes are implemented in this extension study:
 - The SPPB replaced the 6MWT as primary endpoint, the 6MWT changed to a secondary endpoint
 - The 400 meter walk test was removed
 - Echocardiography was eliminated and overall cardiac monitoring was reduced from a level of intense monitoring to one reflecting standard of care following the results of the dedicated profiling cardiac safety study
 - Additional safety monitoring guidance for patients with change in body weight since the core study baseline of +/- 5%
 - Removal of certain central laboratory assessments (i.e. urinalysis, coagulation measurement)
 - e-devices diaries [REDACTED] are replaced by paper diaries which are easier to use for this patient population
- [REDACTED]
- The frequency of the DXA assessment was reduced to a final one at the EOS only

1 Introduction

1.1 Background

CBYM338E2202E1 is a 24-week post-treatment follow-up study of the Phase IIb sarcopenia study CBYM338E2202. This core study is a multi-centered, parallel group dose ranging finding study to assess the effect of 6 monthly doses of bimagrumab on skeletal muscle mass, strength and function in older patients with sarcopenia.

Sarcopenia, the age-associated loss of skeletal muscle mass and physical function ([Cruz-Jentoft et al 2010](#); [Fielding et al 2011](#)), is a common geriatric syndrome with approximately 2-13% of individuals over 65 years and up to 30% of adults over 80 years affected ([Dam 2014](#), [Volpato 2013](#)). While there is no single set of diagnostic criteria for sarcopenia, multiple consensus statements all agree that reductions of muscle mass and gait speed (GS) are the key patient characteristics of sarcopenia with only subtle differences with respect to the recommended cutpoints for each of these measures. More recently, in the first data-driven analysis of older adult subjects, cutpoints were recommended for both of these measures as well as grip strength ([Studenski 2014](#)). The most well accepted sarcopenia criteria at this time are those from the European Working Group on Sarcopenia in Older Persons (EWGSOP) and the Asian Working Group for Sarcopenia, and subjects enrolled in the Phase IIb study in sarcopenia (E2202) must meet the universal thresholds for gait speed and geographic specific thresholds for muscle mass for entry into the study ([Cruz-Jentoft 2010](#)).

Sarcopenia is associated with a myriad of complications, including mobility limitations, an increased risk of falls, fractures and hospitalizations, as well as additional healthcare costs, and increased mortality ([Cruz-Jentoft 2010](#), [Janssen 2004](#), [Visser 2011](#)). In addition, sarcopenic patients frequently require assistance with basic and instrumental activities of daily living (e.g., bathing, shopping) and lose independence. The societal cost of sarcopenia was calculated at over 18 billion US dollars in 2000 ([Janssen 2004](#)).

Currently, there is no pharmacological treatment for sarcopenia and recommended treatment for sarcopenia includes strength training and nutritional optimization (e.g., protein and Vitamin D).

As a potent inhibitor of the Activin Type II receptor (ActRII), bimagrumab blocks the effects of negative regulators of muscle growth including myostatin, activin A, and GDF11 working through this receptor. An accelerated loss of muscle mass, strength and physical function in the large and rapidly growing global aging population represents a substantial, unmet medical need and a novel opportunity for a pharmacotherapeutic that can promote skeletal muscle hypertrophy and improve patient function.

The efficacy and safety of bimagrumab in sarcopenia is currently being evaluated in the CBYM338E2202 core study. The core study protocol and the study design were substantially amended in September 2016, including changes to the primary and some of secondary endpoints.

To maintain consistency with the core study (CBYM338E2202), the Short Physical Performance Battery (SPPB) has become the primary endpoint for this extension trial and several other pertinent functional measures (e.g., 6 minute walk test (6MWT), gait speed (GS), spontaneous physical activity) will be collected as [REDACTED] secondary [REDACTED] endpoints.

1.2 Purpose

The purpose of this extension study (CBYM338E2202E1) is to evaluate the durability of effect on skeletal muscle mass, strength and physical function following 24 weeks of treatment with bimagrumab, in older patients with sarcopenia upon discontinuation of treatment.

The results of this extension study will support the design of a phase III study of bimagrumab treatment for sarcopenia.

[figure not shown]
2 Study objectives

2.1 Primary objective(s)

- The primary objective is to assess the durability of effect of bimagrumab (BYM338) on physical function as measured by the SPPB total score at week 49.

2.2 Secondary objectives

- To evaluate the long term safety effect of bimagrumab following treatment withdrawal as assessed by measures such as vital signs, clinical laboratory variables, electrocardiogram (ECG), and adverse events (AE)
- To evaluate the durability of effect of BYM at week 49 as measured by:
 - 6MWT
 - usual gait speed over 4 meters
 - total lean body mass (LBM) and appendicular skeletal muscle index (ASMI) measured by dual energy X-ray absorptiometry (DXA)

3 Investigational plan

[figure not shown]
3.1 Study design

This Phase IIb extension study is a 24 weeks off drug follow-up observation trial to determine the durability of effect and the safety of bimagrumab in older patients with sarcopenia.

After completing 24 weeks of treatment in the core study (CBYM338E2202 End of Treatment (EOT) visit), newly consenting patients in the extension study CBYM338E2202E1 will continue with the same uniquely identified patient number that was assigned in the core study and will be followed for an additional 24 weeks off drug (see Figure 3-1). They will complete the end of study (EOS) at week 49.

Patients enrolled prior to this amendment #1, will follow the original study design described below Figure 3-2 and will continue to be treated as per the regimen assigned at entry of the extension study. It is anticipated that approximately a total 45 patients will be followed under this design and 10 to 15 of them will still be in the study at the time of implementing this amendment #1.

Figure 3-1 Study design for patients enrolled after the protocol amendment #1

Exercise program

All patients will be requested to continue their home exercise program (2-3 times each week) as it was prescribed and performed in the core study, CBYM338E2202. At the patient's request, the study staff will be able to provide a new set of exercise instructions in order to encourage study participation and adherence.

The exercise program contains activities for muscle strength, endurance, balance and flexibility, as well as warm-up (i.e. walking) and cool-down periods to improve comfort, prepare the body for increased effort, and reduce the risk of training injuries. The exercise program is described in detail in the CBYM338E2202E1 Outcomes Manual.

Week 25/EOT – Joined Core and Extension visit

All EOT assessments of the core study will be performed 4 weeks after the last dose of study drug as outlined in core study CBYM338E2202. Consenting, eligible patients will start in this extension study on the same day (i.e., EOT visit of CBYM338E2202).

The ability and willingness of the patient to continue performing the home-based exercise program should be re-assessed by the investigator or a team member during this visit.

For a complete list of assessments, please refer to Section 6 [Table 6-1](#).

Subsequent Visits – Weeks 29-45

Between the extension study entry visit (week 25) and the EOS (week 49), newly enrolled patients will only visit the site once for the week 37 visit. In between the visits, the patients will be contacted monthly by phone by the site personnel to enquire on the patient's health status and to check compliance with the  diaries.

For a complete and detailed list of assessments, please refer to [Section 6](#) and [Table 6-1](#).

End of study (EOS)/Week 49

This is the last planned visit in the study. It will take place at week 49 or earlier in case of premature study discontinuation.

Following the EOS visit, the patient will be followed by his/her treating physician according to the local standard of care and the patient's situation.

For a complete and detailed list of assessments, please refer to Section 6 [Table 6-1](#).

[figure not shown]
[figure not shown]

Figure 3-2 Study design for patients enrolled prior to protocol amendment #1

Management of patients enrolled prior to the protocol amendment #1

Patients enrolled prior to the study amendment #1 will continue to be dosed every 4 weeks until week 49 (EOT) and will then have a 4 weeks follow-up period until week 53 (EOS).

These patients will also continue the exercise program described above.

Please refer to [Section 6](#) and the specific [Table 6-2](#) for a complete and detailed list of assessments for these patients.

3.2 Rationale of study design

The aim of developing bimagrumab therapy in elderly adults with sarcopenia is to enable them to increase their physical function to a certain level that they could afterwards maintain without any support other than regular exercise and potentially vitamin D supplementation. This extension study is the natural follow-up of the patients treated for 24 weeks in the core study; it will evaluate the changes in physical function of this patient population over 24 week off-treatment period as well as assess the overall long-term safety of bimagrumab.

The study population will be comprised of men and women aged 70 years or older with sarcopenia who participated in the core study CBYM338E2202. Only patients who complete the 24 weeks of treatment in the core study will be eligible for this study given the purpose to evaluate the durability of 24-week therapy. Of the 293 patients expected to enroll in the core

study, it is expected that approximately 200 patients will be eligible and will agree to participate in this extension study.

Although patients enrolled under this amendment will not receive any investigational drug as part of this extension, they will have a standardized exercise program. The schedule of two to three exercise sessions per week will be maintained throughout the studies (core and extension) and will serve as a standard of care together with the vitamin D supplementation.

The code of the treatment received in the core study will remain blinded to sites and patients for the entire study duration including this extension study. This will avoid a potential reporting bias that patients and site staff may otherwise have when assessing physical function, mobility or reporting safety.

In line with the primary endpoint used in the core study, the extension will use the SPPB total score as the primary endpoint. The SPPB score and 4-meter gait speed have emerged as the predominant measures that characterize impaired lower extremity function in older adults in general and in those with sarcopenia and frailty ([Studenski et al 2014](#)).

As the natural follow-up of the core study population, a number of efficacy (e.g. SPPB, [REDACTED]) or safety (vital signs, laboratory measurements, cardiac adjudication) assessments are being carried over in the extension study in order to fully evaluate the patient journey over approximately a 1 year period. Given the absence of required monthly drug infusion, the frequency of the visits is reduced in comparison to the core study in order to limit patients' burden. However, in order to maintain patient's compliance and avoid under-reporting of events such as [REDACTED] monthly phone calls to the patients will be performed.

As patients enrolled prior to the protocol amendment #1 will differ (e.g. placebo effect) from patients newly enrolled in the extension, it was decided to keep them on their 4-weekly dosing regimen as originally designed, to maximize the understanding of these regimen. They will therefore follow a different visit schedule.

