9.6 Interim analyses

An interim analysis will be triggered by the analysis of the core study Part A. Data from primary and key secondary efficacy parameters will be summarized. This interim analysis will provide a preliminary evaluation of endpoints over approximately 12 months; and together with core study Part A data will support next step decision making.

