### **3.8 Interim analyses**

An interim analysis will be triggered by the analysis of the core study Part A. Data from primary and key secondary efficacy parameters will be summarized. The interim analysis will provide a preliminary evaluation of endpoints over approximately 12 months; and together with core study Part A data will support next step decision making. Analyses based on PP set will not be included for IA.

The interim analysis will cover following analyses:

- Patient disposition
- Analysis sets
- Demographics and patient characteristics at Week 25 (nutritional status, protein intake, 6MWT, SPPB total score, Gait Speed, [REDACTED], and ASMI)
- Treatments (Study drug for population I, prior and concomitant medication for both populations)

- Primary analysis: SPPB at Week 49, summaries of population I and II separately
- Secondary analyses: 6MWT, Gait speed, LBM and ASMI, summaries for population I and II separately

- █ [REDACTED]
- Safety analyses:
    - Nutrition status/protein intake
    - Population I: TEAE, ECG, Vital sign, and notable Lab
    - Population II: notable Lab.
  - Supportive analysis:
    - Proportion of sarcopenic patients at Week 25 vs Week 49.

█ [REDACTED] Such analysis will be detailed in a separate document when it becomes necessary and/or be generated for the final analysis.

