### 3.8.1 Interim Analysis FIR

Among the outputs planned to be released for the IA, key statistical outputs listed below will be released in priority:

- Summary of patients disposition by treatment
- Summary of patients under each analysis set by treatment
- Summary of demographic characteristics by treatment
- Summary of patient characteristics at Week 25 (6MWT, SPPB total score, Gait Speed, █ [REDACTED], and ASMI) by treatment.
- Analysis of primary endpoint: SPPB at Week 49 for both populations.
- In addition to primary endpoint, statistical summary from Week 25 to Week 49 performance along with figures of time course and/or change from Week 25 will be provided for following endpoints (secondary endpoints) for both populations:
  - 6 minute walk test (6MWT)
  - SPPB total score
  - Gait Speed (GS)

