## 5.4 Definition of Baseline and post-baseline measurements

Baseline is defined as the core study baseline, for both populations. In the planned analyses, Week 25 has been referred to majority of the time, and it is referring to a relative baseline to the extension study, which is defined as the Visit 1 pre-dose assessments of the extension study (Week 25, EOT visit of the core study) for population I and for population II defined as the Visit 1 assessments of the extension study (Week 25, EOT visit of the core). This visit will be labeled as Week 25 in the reports.

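### No visible efficacy analysis measures Week 49 against the core baseline, so the share of the on-treatment gain that patients keep is not estimated

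*Protocol*

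**What the plan says.** Protocol 3.2 gives the aim of the programme: patients should "increase their physical function to a certain level that they could afterwards maintain without any support other than regular exercise". It explains that efficacy and safety assessments are carried over from the core study "in order to fully evaluate the patient journey over approximately a 1 year period". The same section also states a narrower aim for the extension: "it will evaluate the changes in physical function of this patient population over 24 week off-treatment period".

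On the interim, Protocol 9.6 says "This interim analysis will provide a preliminary evaluation of endpoints over approximately 12 months", and SAP 3.8 repeats this almost word for word. Both add that the results will be used together with core Part A data. The Amendment 1 rationale says "Data from this extension study will be combined with the core study data and will enable decision making on the rest of the program".

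SAP 5.4 states "Baseline is defined as the core study baseline, for both populations", then notes that most planned analyses refer to Week 25 as a relative baseline for the extension. The priority interim outputs in SAP 3.8.1 are a "statistical summary from Week 25 to Week 49 performance along with figures of time course and/or change from Week 25". The primary endpoint (Protocol 9.4.1, SAP 3.4) is the SPPB total score at Week 49. There is no formal hypothesis test.

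**The concern.** Durability means that some of a gain is kept. To say how much, three levels are needed: before treatment, at the end of treatment and after the off-drug period. The visible plan uses the last two. It defines the first as baseline and then does not use it as the reference for any Week 49 efficacy result.

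The core study report does not fill the gap. Protocol 3.2 expects about 200 of 293 core patients (200/293 = 68%) to enter the extension, all of them treatment completers who agreed to continue. The core baseline mean of all core patients need not be that of the extension patients.

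What is at stake is interpretation. Protocol 1.2 says the results will support the design of a phase III study, and the interim feeds next-step decisions. A reader who sees a Week 49 mean one point below Week 25 would not know whether patients are still above where they started.

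**Working it through.** **1. The plan's own precision figure.** Protocol Table 9-2 (SAP Table 3-1) is reproduced by 1.96 × SD/√n. For SD 2.0: 1.96 × 2.0/√50 = 0.55 and 1.96 × 2.0/√40 = 0.62. All eight cells match. The table describes a single-arm SPPB mean and is not in dispute.

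**2. The reference used by each visible efficacy output.**

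| Place | Output | Reference |
|---|---|---|
| Protocol 9.4.2, SAP 3.4.1 | Raw Week 49 SPPB by arm | None |
| SAP 3.4.2 | Population I: continued dose versus switched placebo, Week 49 values | Other arm, same visit |
| SAP 3.4.4 | Proportion sarcopenic at Weeks 25 and 49 | Core entry thresholds for gait speed and ASMI |
| SAP 3.5.2, 3.5.3.1, 5.8.1 | By-visit summaries, plots and t-test intervals | Visits from Week 25 on (SAP 5.5.1) |
| SAP 3.8.1 | Interim time courses | Week 25 |
| SAP 3.5.3.1, 5.8.2 | Population II ANCOVA, exploratory, final analysis only | Week 25 covariate |
| SAP 3.2.2.2.2 | Week 25 tables of SPPB, LBM and ASMI, with an unclear mention of a baseline value | Entry characteristic; no Week 49 value |

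None is Week 49 against core baseline.

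**3. What this can and cannot separate.** Illustrative SPPB means for a single arm (assumed values):

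| Course | Core baseline | Week 25 | Week 49 | Week 49 − Week 25 | Week 49 − core baseline |
|---|---|---|---|---|---|
| Gain fully kept | 7 | 8 | 8 | 0 | +1 |
| Same gain fully lost | 7 | 8 | 7 | −1 | 0 |
| Gain half kept | 7 | 9 | 8 | −1 | +1 |
| Full return | 8 | 9 | 8 | −1 | 0 |
| No gain at all | 8 | 8 | 8 | 0 | 0 |

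Rows 1 and 2 differ on Week 25 to Week 49 data. Rows 3 and 4 do not, and neither do rows 1 and 5. Only core baseline separates those pairs.

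**4. Why the Population II placebo contrast does not supply the retained benefit.** Adjusted difference = (difference at Week 49) − slope × (difference in covariate). Assume bimagrumab means of 9 at Weeks 25 and 49, placebo means of 8 at both, equal core baselines and a slope of 0.7.

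- Adjusted for Week 25: 1.0 − 0.7 × 1.0 = 0.3.
- Adjusted for core baseline: 1.0 − 0.7 × 0 = 1.0.

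A fully kept 1.0-point benefit appears as 0.3 in the planned model. That model estimates divergence after stopping, given the Week 25 level.

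**5. Precision of the added estimates.** The documents give no correlation ρ between core baseline and Week 49, so 0.3 to 0.8 is an assumption.

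*Within-arm change:* half-width = 1.96 × SD × √(2(1−ρ))/√n. With SD 2.0:

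| n per arm | ρ = 0.3 | 0.5 | 0.7 | 0.8 |
|---|---|---|---|---|
| 50 | 0.66 | 0.55 | 0.43 | 0.35 |
| 40 | 0.73 | 0.62 | 0.48 | 0.39 |

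The factor √(2(1−ρ)) is 1 at ρ = 0.5, which returns Table 9-2. Over SD 1.5 to 3.0, the range is 0.26 to 1.10.

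*Bimagrumab minus placebo at Week 49* (equal arms and SD 2.0 assumed): unadjusted, 1.96 × 2.0 × √(2/n) = 0.78 at n = 50 and 0.88 at n = 40. Adjusting for core baseline multiplies this by √(1−ρ²), which is 0.95 at ρ = 0.3 and 0.60 at ρ = 0.8. The result is 0.75 to 0.47 at n = 50 and 0.84 to 0.53 at n = 40.

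*Smaller arms:* Protocol 4 expects 200 entrants and 30% dropout, and about 45 patients belong to Population I. With four equal arms (assumed), (200 − 45) × 0.7/4 ≈ 27. At n = 27 the adjusted contrast has a half-width of 1.02 (ρ = 0.3) to 0.64 (ρ = 0.8), and the within-arm change 0.89 to 0.48.

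**The case against.** A reader might infer that every efficacy analysis starts at Week 25 and that retention cannot be told from loss. The documents do not support either reading.

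- The primary endpoint is a raw Week 49 score. In Population II it is shown by core arm, placebo included, which is an indirect reference.
- Sarcopenic status at Week 49 is judged by the core entry criteria for gait speed and ASMI, and the interim includes this output.
- Full retention and full loss of a given gain do separate on Week 25 to Week 49 data.

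The one-year wording can also be over-read. In Protocol 3.2 it explains why assessments are carried over and does not specify an analysis. The 12-month wording is tied to use alongside core Part A data, Week 49 is Month 13 in Table 6-1, and Protocol 3.2 also states a 24-week aim.

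Absence is hard to prove here. Bullets under SAP 3.4.4 and 3.5.4 and text after the ANCOVA are redacted, and SAP 5.4 says only that most analyses refer to Week 25. The Week 25 tables may show core baseline values for the extension patients.

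Finally, within-arm change from core baseline is open to confounding. Patients entered on low gait speed and all of them exercise, so regression to the mean and training contribute to it.

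All of this stands, and it narrows the point without removing it. The sarcopenia proportion is a yes/no measure of two other variables and says nothing about retained SPPB. The raw Week 49 comparison involves selected completers with no adjustment for pre-treatment level. The stated intention to combine core and extension data is not turned into any visible efficacy analysis. The confounding argument affects which added estimate should lead.

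**Conclusion.** The point holds in a limited form. No visible analysis measures Week 49 against the baseline that SAP 5.4 defines, and the only covariate-adjusted placebo contrast in the off-drug population conditions on a value that already carries the core treatment effect. Within an arm, the plan therefore cannot separate partial retention from full return, or a kept gain from no gain, and it does not estimate the share of benefit retained.

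A reader might also infer that the added analysis is free in precision. That is so only if the core baseline to Week 49 correlation is at least 0.5, and the documents give no correlation. With SD 2.0 and n 40 to 50, the within-arm half-width is about 0.35 to 0.73, below the 1.0-point relevant change in Protocol 6.3.2. At about 27 per arm, the placebo contrast could reach about 1.0.

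The conclusion rests on the unredacted text. The study is descriptive, so no test is invalid; this is an inexpensive gap that should be closed.

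**What to change.** In SAP 3.4.1, 3.5.2, 3.5.3.1/5.8.2 and 3.8.1:

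- Link the core data on the patient number, which Protocol 3.1 keeps unchanged, and show core baseline as the first time point for extension patients in the by-visit tables and plots.
- Report change from core baseline to Weeks 25, 37 and 49 (DXA at the visits where it is done) with 95% CIs, by core arm for Population II and by extension arm for Population I.
- As the main added estimate, report for Population II the bimagrumab-minus-placebo difference at Week 49 adjusted for core baseline instead of Week 25. The planned Week 25-adjusted model can stay, labelled as divergence after stopping.
- Label within-arm change, and the proportion at least 1.0 SPPB point above core baseline, as descriptive, because exercise and regression to the mean also affect them.
- State that all these estimates use observed data from core completers who consented, so randomisation protects the placebo contrast only in part.

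If a redacted section already contains this analysis, a cross-reference from SAP 5.4 is enough.

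The cost is one merge with the core database and a few extra table columns. No new data or visits are needed.
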